10.4.2 Analysis of the Primary Efficacy Endpoint(s)

The two primary outcomes are to test the hypotheses that each of the BWL+VOUCHER and BWL+HOME interventions will result in better weight loss at week 24 compared to BWL-Alone. The primary analysis is an intention-to-treat, between-group comparison of the mean change from baseline (randomization) to week 24 using a linear mixed model. Specifically, we will regress the mean change from baseline on the treatment indicator and baseline weight loss. Significance will be determined using an α cutoff of 0.05. The primary analysis will be an intent-to-treat analysis. The model will include each participant as a random intercept to adjust for within-patient correlation of the repeated measures, fixed predictors of study arm indicators, time indicators, and time by study arm interactions. In addition, sensitivity analyses will be conducted adjusting the model by including baseline variables that either had between-group differences at baseline or that were associated with the likelihood of missing outcomes at a 0.20 significance level.

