5.5 Measures to Minimize Bias: Randomization and Blinding

A permuted block randomization method will be used to assign participants to one of the three intervention groups in a 1:1:1 ratio. Once eligibility is confirmed, intervention assignment will be made by a pre-programmed randomization scheme. Block sizes will be varied to minimize potential bias, and randomization will be stratified by baseline SNAP/WIC receipt (vs no receipt). All participants who are randomized will be entered into the study database and analyzed according to Consolidated Standards of Reporting Trials guidelines for multi-arm parallel-group randomized trials.¹¹¹ This is an open-labelled randomized trial.

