- Review of medications
- Waist circumference
- Blood pressure and heart rate
- Urine pregnancy test (if unsure about pregnancy status)
- Questionnaires
 - Demographic data
 - Short Form-36 (SF-36)
 - Impact of Weight on Quality of Life-Lite (IWQOL-Lite)
 - US Adult Food Security Survey, 10 item
 - Eating Disorder Examination Questionnaire (EDE-Q)
 - Patient Health Questionnaire 8 (PHQ-8)
 - Eating Behavior Inventory (EBI)
 - Eating Self-Efficacy Survey
 - Perceived Nutrition Environment
 - Neighborhood Environment Walkability Scale
- 24-hour dietary recall interview
- Skin carotenoid assessment
- A second 24-hour dietary recall will be scheduled within 7 days and will need to be completed before the participant is randomized.

Randomization visit. The randomization visit will occur within two weeks of the second dietary recall (scheduled within 7 days after the baseline assessment visit). For randomized participants, the first BWL visit will also occur at this visit.

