9 STUDY ASSESSMENTS

9.1 Efficacy Assessments

Research staff will conduct assessments at our Center at weeks 0 (baseline), 12 and 24. All measures will be administered at all timepoints. Assessment staff will receive training in adherence to the data collection protocol. Questionnaires will be completed on REDCap, a secure, web-based program (if requested, participants can completed questionnaires on paper). To provide compensation for time and travel, participants will be paid \$40 per assessment. We will provide participants with ClinCards, which are similar to debit cards, that we have used for other studies. This form of payment allows us to load money remotely, enabling us to compensate participants soon after they complete study tasks.

Demographic and neighborhood data. Standard questionnaires will be administered to collect data on demographics at week 0 including age, biological sex, gender, race/ethnicity, income, street address, zip code, receipt of SNAP and/or WIC, household size, disabilities, marital status, and highest education level. We will recollect these data at weeks 12 and 24 to account for changes in status. We will also collect descriptive data at each timepoint on neighborhood food and physical activity environment including the Perceived Nutrition Environment Measures Survey¹³³ and Neighborhood Environment Walkability scale.¹³⁴

Weight and height. Weight will be measured in light clothes and no shoes, after an 8-hour fast, using a standardized scale calibrated monthly and accurate to 0.1 kg. Weight will be measured in duplicate. Height will be assessed in duplicate with a wall-mounted stadiometer at baseline.

Quality of life. General health-related quality of life (HRQOL) will be assessed by the Short Form (SF)-36, which contains 36 items that measure subjective health status.¹¹⁹ The scale forms two summary measures—a physical and mental component summary. Scores are transformed using a 0 to 100 scale, with higher scores indicating better HRQOL. Weight-related quality of life will be measured with the 31-item IWQOL-Lite scale.¹²⁰ The measure generates a total score ranging from 0 (worst) to 100 (best).

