10.2 Sample Size Determination

This is an exploratory study. The sample size should be sufficient to provide us with effect size estimates for a larger randomized controlled trial.

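### The primary model adjusts for a baseline quantity that is zero for everyone and leaves out SNAP/WIC receipt, the factor used to stratify randomization

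*Combined protocol and SAP*

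**What the plan says.** Section 10.4.2 describes the primary analysis as a "between-group comparison of the mean change from baseline (randomization) to week 24 using a linear mixed model". The next sentence gives the regression: "we will regress the mean change from baseline on the treatment indicator and baseline weight loss". The section then adds the repeated-measures structure: "The model will include each participant as a random intercept to adjust for within-patient correlation of the repeated measures", with fixed effects for arm, time and their interaction. Other baseline variables enter only in sensitivity analyses, and only if they differ between arms or are associated with missing outcomes at the 0.20 level.

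On weight measurement, Section 9.1 states: "Research staff will conduct assessments at our Center at weeks 0 (baseline), 12 and 24". Section 6 places the pre-treatment weight at the screening visit. Of the later randomization visit it says "For randomized participants, the first BWL visit will also occur at this visit", and it lists no further weight there.

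On allocation, Section 5.5 states that "randomization will be stratified by baseline SNAP/WIC receipt (vs no receipt"). Section 9.1 lists "receipt of SNAP and/or WIC" among the week 0 demographic items. Sections 10.4.1 to 10.4.3 do not mention SNAP or WIC.

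**The concern.** There are two separate faults in the specification.

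1. **The covariate carries no information.** A change score is zero at its own origin. If baseline is randomization, weight lost at baseline is zero for all 105 participants. The term looks like a slip for baseline weight, but this is the sentence that defines the primary model. It also says only mean change, while the endpoint in Section 3 is percent of initial weight. With both the covariate and the response scale unclear, two analysts could fit different models and each claim to follow the plan.

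2. **The stratification factor is missing.** Stratified blocks balance SNAP/WIC receipt across arms. An analysis that ignores the stratum leaves its variance in the residual, so the reported standard error exceeds the true one under this design. Intervals are then too wide and the test is conservative. Section 10.2 gives the study's purpose as follows: "The sample size should be sufficient to provide us with effect size estimates for a larger randomized controlled trial". The estimates themselves are not distorted, but their reported precision would be understated to whoever plans the next trial.

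**Working it through.** The plan gives no power, effect size, SD or dropout rate for its 105 participants, so there is no figure of its own to reproduce.

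**Is there any other value for the covariate?** Study weights are taken at weeks 0, 12 and 24 (Section 9.1). No second pre-treatment weight is listed for the randomization visit (Section 6). Earlier weight loss appears only as an exclusion threshold, more than 5 kg in the previous 90 days (Section 5.2), and is not named as a covariate. The documents therefore define no non-zero value.

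**Rank of the design matrix.** With an intercept, two arm indicators and a column of zeros, there are 4 columns and the rank is 3. In the repeated-measures form (intercept, arm, time, arm by time; weeks 12 and 24; 35 per arm), the rank is 6 with 6 columns and still 6 once the zero column makes 7. The coefficient cannot be estimated and nothing is adjusted.

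**Could the stratum enter by another route?** In 20,000 stratified randomizations at each of 30% and 50% SNAP/WIC receipt (assumed, with blocks of 3 and 6), the chi-square p-value for stratum by arm never fell below 0.79. With larger assumed blocks, of up to 12, it stayed above 0.63. The imbalance rule would in effect never select it. The missingness rule leads only to a sensitivity analysis, and only if SNAP/WIC receipt happens to predict missing outcomes.

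**Cost of omitting the stratum.** Let R² be the share of outcome variance that the stratum explains. It is not in the documents, so a range is assumed.

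- Ratio of standard errors, omitted to included: k = 1/√(1 − R²). At R² = 0.10, k = 1/√0.90 = 1.054.
- Actual two-sided error of a nominal 5% test: 2 × [1 − Φ(1.96 k)]. At R² = 0.10, 2 × [1 − Φ(2.066)] = 0.039.
- Power by the noncentral t, with 35 per arm, total SD 1 and a standardized difference of 0.68. That difference is assumed; it gives about 80% power at this sample size. The noncentrality is 0.68 × √(35/2) × k. The critical value is multiplied by k when the stratum is omitted.

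| R² | SE overstated by | Actual error | Power with stratum | Power without | Difference (points) |
|---|---|---|---|---|---|
| 0 | 0% | 5.0% | 80.4% | 80.4% | 0 |
| 0.02 | 1.0% | 4.8% | 81.2% | 80.7% | 0.5 |
| 0.05 | 2.6% | 4.4% | 82.4% | 81.1% | 1.4 |
| 0.10 | 5.4% | 3.9% | 84.4% | 81.7% | 2.7 |

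Differences are taken before rounding.

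**Simulation.** A single week-24 outcome was simulated with 105 participants, no dropout, blocks of 3 and 6 within stratum, and 40,000 runs per cell. Without the stratum at R² = 0.10, the error was 0.0388 at 50% receipt and 0.0406 at 30%, and the power difference was 2.8 points at both. With the stratum in the model, the error was 0.049 to 0.051. A second simulation, with 4,000 trials per cell and a difference of 0.67, gave errors of 0.038 to 0.041 at R² = 0.10. Stronger assumed strata gave 0.028 to 0.031 at R² = 0.20 and 0.018 to 0.022 at R² = 0.30.

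These figures apply to the stratum only. Baseline weight is not a stratification factor, and the documents give no correlation between it and percent change.

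**The case against.** The strongest reply concerns importance, since the text itself is not in dispute. A column of zeros simply drops out of the fit. The arm, time and interaction terms are untouched, and the randomized contrasts remain unbiased. The lead fault therefore has no demonstrated effect on the result. The second fault is conservative and small at plausible values of R², and R² = 0 lies within the range. Power without the stratum never drops below 80.4%, so the difference is a gain forgone, and an exploratory study has no power target to miss. The sampling error of an estimated SD on 102 degrees of freedom is about 1/√(2 × 102) = 7%, larger than the 5.4% overstatement at R² = 0.10. Finally, the calculation uses one week-24 outcome without dropout, whereas the plan has a repeated-measures model and expects missing data.

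Most of this stands as a limit on size. The power figures compare the planned model with an adjusted one and do not show a fall below any stated target. All of the magnitudes are illustrative. It is also right that the authors must confirm which covariate they meant.

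It does not remove the point. The sampling error of an SD is unavoidable; overstating the standard error by leaving out a known design factor is avoidable. That no bias results does not excuse a primary model that cannot be fitted as written.

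**Conclusion.** Both faults hold. The covariate error is definite and rests on the text alone: as written, the intended baseline adjustment does not take place. Its cost in precision cannot be computed from the documents. The omission of the stratum is also certain from the text, and its effect is small to modest: none at R² = 0, rising to a standard error 5.4% too large and a true test level of 3.9% at R² = 0.10. Those sizes depend on assumed values for R², SNAP/WIC prevalence, block sizes and the standardized difference, and on a two-sided 5% level. Neither fault biases the arm comparisons or inflates type I error. The plan should be corrected before the data are analysed, because the remedy is a matter of wording.

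**What to change.** In Section 10.4.2:

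- Replace the undefined covariate with baseline weight in kg, after the authors confirm that this was intended.
- Add the SNAP/WIC stratum (yes/no) as a prespecified fixed effect.
- Keep the participant random intercept and the arm, time and arm-by-time terms.
- State that the response is percent change from baseline weight and that the estimates are the week-24 arm contrasts.

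In Section 10.4.3, use the stratum and the baseline value of each outcome in the secondary models. As a minor point, align Section 10.4.1 with Section 10.4.2, so that covariates picked by baseline tests stay in sensitivity analyses and do not enter the primary model.

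The cost is wording plus two degrees of freedom. Both variables are collected at week 0. Section 5.1 makes completing the baseline assessments a condition of entry, so missing covariate values should be rare.

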4 STUDY PLAN

4.1 Study Design

The single-site, open-label, phase 2, three-arm RCT will enroll 105 participants recruited from the community who will be randomly assigned to one of three groups, all of which will receive BWL. Groups include: BWL-Alone (including standard-of-care referral and connection with community food resources); BWL combined with food vouchers (BWL+VOUCHER); and BWL combined with home-delivered, medically tailored groceries (BWL+HOME). Each intervention will be provided for 24 weeks. We hypothesize that participants in BWL+VOUCHER and BWL+HOME will achieve greater improvements in weight, self-reported and objective markers of dietary quality, and health-related quality of life relative to BWL-Alone. Further, we predict that participants in BWL+HOME will experience greater improvements in weight, dietary quality, and quality of life than BWL+VOUCHER. Assessments will occur at weeks 0, 12, and 24.

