10.4.3 Analysis of the Secondary and Exploratory Endpoint(s)

For non-primary comparisons, an α level of 0.05 will be used for significance. We will test the main effects of treatment condition on percent initial weight change at skin carotenoid levels, general health and weight-related quality of life as well as exploratory endpoints using linear mixed models and similar methods as described above. Analyses will use intention-to-treat analyses and will be conducted with and without adjustment for baseline differences in characteristics. We plan to assess for differential effects of the interventions based on sex/gender and race/ethnicity. Separate analyses will be performed for men and women and based on self-identified race/ethnicity, although these will be considered exploratory as there is no strong reason to hypothesize a difference in efficacy based on these characteristics.

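### The only covariance feature named for the primary model is a random intercept; with one residual variance, the week-24 standard error is right only if weeks 12 and 24 have equal spread

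*Combined protocol and SAP*

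**What the plan says.** Section 10.4.2 plans an intention-to-treat comparison of change from baseline to week 24, each food arm against BWL-Alone, by linear mixed model. One sentence gives the regression: "Specifically, we will regress the mean change from baseline on the treatment indicator and baseline weight loss". A later sentence gives the covariance: "The model will include each participant as a random intercept to adjust for within-patient correlation of the repeated measures". It then lists the fixed effects: "fixed predictors of study arm indicators, time indicators, and time by study arm interactions". The threshold is set by "Significance will be determined using an α cutoff of 0.05", with sidedness not stated.

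Section 4.1 says "Assessments will occur at weeks 0, 12, and 24" and section 9.1 says "All measures will be administered at all timepoints", so weight is measured at two post-baseline visits. Section 10.4.2 does not say whether the response rows are weeks 12 and 24 only or also week 0. It does not say whether the residual variance may differ by visit. It mentions neither an unstructured covariance nor robust standard errors.

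Sections 1.1, 3 and 10.1 define the primary endpoint as percent of initial weight lost; the model description in 10.4.2 speaks only of change. Section 10.2 gives no SD, effect size or power. It states the purpose of the trial instead: "The sample size should be sufficient to provide us with effect size estimates for a larger randomized controlled trial". Section 10.4.3 tests main effects of treatment on the secondary and "exploratory endpoints using linear mixed models and similar methods as described above".

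**The concern.** A participant random intercept with a single residual variance forces the same variance on every visit. The primary question concerns week 24 alone. If the spread of weight change differs between weeks 12 and 24, the model gives the week-24 contrast a variance borrowed partly from week 12. The primary p-values and interval widths then depend on a visit that is not part of the primary question. The trial is meant to supply effect size estimates for a larger trial, so the interval around the week-24 difference is one of its main products.

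The covariate adds a second problem. Baseline weight loss is not defined, and if loss is measured from randomization it is zero for every participant and adjusts for nothing.

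**Working it through.** **Inputs from the documents.** 105 participants, 35 per arm (sections 1.1 and 4.1); assessments at weeks 0, 12 and 24 (section 4.1); α = 0.05 (section 10.4.2), taken as two-sided. The plan has no standard error, SD or power figure to reproduce.

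**Assumed inputs.** r = SD(week 12)/SD(week 24) from 0.7 to 1.1. The standard errors and half-widths use a week-24 SD of 6 percentage points. The checks use a week 12–24 correlation of 0.6 or 0.8. None of these is in the documents.

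**Conditions.** Response rows are change at weeks 12 and 24; arm-by-visit means are fitted; there is one residual variance, complete data and no covariate. Once a baseline covariate is included, r is the ratio of residual SDs.

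**Closed form.** Under these conditions REML estimates the common variance as the average of the two visit variances. With n per arm:

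- Model SE = sqrt(((SD12² + SD24²)/2) × 2/n)
- Correct SE = sqrt(SD24² × 2/n)
- Ratio = sqrt((1 + r²)/2)
- Two-sided type I error = 2 × (1 − Φ(1.96 × ratio))

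At r = 0.7 the ratio is sqrt((1 + 0.49)/2) = 0.863, and the type I error is 2 × (1 − Φ(1.692)) = 9.1%.

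At the assumed SD of 6, the correct SE is 6 × sqrt(2/35) = 1.434 and the correct 95% half-width is t(0.975, 102) × 1.434 = 1.9835 × 1.434 = 2.84 points. The last column multiplies that half-width by the ratio.

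| r | SE ratio | SE error | Type I error | 95% CI coverage | Model SE | Half-width |
|---|---|---|---|---|---|---|
| 0.7 | 0.863 | −13.7% | 9.1% | 90.9% | 1.238 | 2.46 |
| 0.8 | 0.906 | −9.4% | 7.6% | 92.4% | 1.299 | 2.58 |
| 0.9 | 0.951 | −4.9% | 6.2% | 93.8% | 1.364 | 2.71 |
| 1.0 | 1.000 | 0% | 5.0% | 95.0% | 1.434 | 2.84 |
| 1.1 | 1.051 | +5.1% | 3.9% | 96.1% | 1.508 | 2.99 |

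**Check by fitted models.** Ten REML fits (35 per arm, three arms, sample moments set exactly, correlations 0.6 and 0.8) gave the model SEs in the table at both correlations, matching the closed form to three decimals.

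**Check by simulation.** With 20,000 complete-data trials per cell, the random-intercept model rejected in 9.3–9.4%, 7.3–7.7%, 6.2–6.3%, 4.9–5.0% and 4.1–4.3% of trials at r = 0.7, 0.8, 0.9, 1.0 and 1.1. With the week-24 variance, as under an unstructured covariance, the rate was 4.8–5.3% throughout.

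**Visit-averaged effect.** For the mean of the two visits, the random-intercept variance per participant is (average visit variance + covariance)/2 = (SD12² + SD24² + 2cov)/4. That is the true variance at every r, so a treatment effect averaged over visits carries no such error.

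**The case against.** A reader might infer that section 10.4.2 specifies two incompatible primary models, because a random intercept and time terms cannot be fitted to one row per person. The text does not support that. It names a linear mixed model, then elaborates on the model with a definite article, which reads naturally as one model loosely described. A merged version, with change on arm, a baseline term, time and arm-by-time plus a random intercept, can be fitted.

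The stronger objection is that the harm rests on things the plan does not state: r, a single residual variance, and week 0 not being a response row. A random intercept does not rule out visit-specific residual variances or a robust standard error, and either would remove the problem. This stands as a limit on the size of the claim. It does not remove the point, because the random intercept is the only covariance feature named and the plan adds neither remedy.

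The complete-data condition is also a real limit, since sections 8.3 and 10.4.1 anticipate missing outcomes. The assumed range has three values of r below 1 and one above, so the table should not be read as a forecast of inflation. Finally, section 10.2 calls the study exploratory. That lowers the stakes of the p-values but not of the intervals, and a 0.05 cutoff is still set.

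**Conclusion.** The concern holds in a limited form. Section 10.4.2 leaves the response rows open, uses an undefined covariate, and names a covariance feature which, with one residual variance on change at weeks 12 and 24, gives a correct week-24 standard error only at r = 1. The error is zero there and about 5% of the standard error at r = 0.9 or 1.1. At r = 0.7 it reaches −13.7%, with type I error 9.1%. These figures assume complete data, no covariate and a common variance across arms. If week 0 is also a response row they do not apply, and the week 12–24 correlation then matters too.

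Three further inferences are not supported:

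- **That the primary tests are anticonservative.** The documents give no SDs, so the direction is unknown.
- **That the estimated effect is biased.** With complete data the point estimate is the same under either covariance.
- **That every secondary and exploratory result inherits the error.** Section 10.4.3 literally refers to main effects of treatment, and a visit-averaged effect does not carry it. The concern reaches those endpoints only where a week-24 contrast is tested.

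The change is worth making before analysis because it removes the dependence on r at almost no cost.

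**What to change.** In section 10.4.2, state one model:

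- Response rows: percent change from initial weight at weeks 12 and 24.
- Fixed effects: arm, visit, arm-by-visit and baseline body weight, the last replacing baseline weight loss.
- Covariance: unstructured for the two visits, in place of the random intercept, with Kenward-Roger or Satterthwaite degrees of freedom.
- Primary tests: the two week-24 contrasts, BWL+VOUCHER and BWL+HOME each against BWL-Alone.

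In section 10.4.3, use the same covariance wherever a week-24 contrast is tested.

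**Cost.** Wording and one extra covariance parameter; no change to visits, data collection or sample size. If the two SDs are equal, the loss is in degrees of freedom only. The random intercept has 204/(1 + ρ²), which is 150 at ρ = 0.6 and 124 at ρ = 0.8, against 102 for the unstructured model. The interval widens by 1.9835/1.9759 (0.4%) to 1.9835/1.9793 (0.2%). If the SDs differ, the interval moves to its correct width: at the assumed SD of 6, from 2.46 to 2.84 at r = 0.7, or from 2.99 down to 2.84 at r = 1.1.

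### The stratification factor (SNAP/WIC receipt) is in none of the planned models; if it predicts the outcome, standard errors are slightly too large and tests slightly conservative

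*Combined protocol and SAP*

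**What the plan says.** Section 5.5 of the combined protocol and SAP uses permuted blocks of varied size, 1:1:1, and states that "randomization will be stratified by baseline SNAP/WIC receipt (vs no receipt").

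Section 10.4.2 describes the primary model twice. First, "we will regress the mean change from baseline on the treatment indicator and baseline weight loss". Then it gives a random intercept per participant with "fixed predictors of study arm indicators, time indicators, and time by study arm interactions". Neither description contains the stratum. Covariates enter only a sensitivity analysis, by "including baseline variables that either had between-group differences at baseline" or variables "associated with the likelihood of missing outcomes at a 0.20 significance level". Section 10.4.1 adds that key baseline variables differing by arm will be considered as covariates.

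Section 10.4.3 analyses the secondary and exploratory endpoints "using linear mixed models and similar methods as described above", with and without adjustment for baseline differences. It does not name the stratum either.

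Section 9.1 collects "receipt of SNAP and/or WIC" at week 0 and adds: "We will recollect these data at weeks 12 and 24 to account for changes in status".

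**The concern.** Stratified blocks make the arms nearly equal in SNAP/WIC receipt, so a stratum effect on weight change largely cancels from the arm contrast. A model without the stratum still counts that variation as residual. Its standard error then describes a less precise trial than the one that was run.

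Intervals are a little wide and tests a little conservative if the factor is prognostic. Section 10.2 says the trial is meant to supply effect size estimates for a larger trial, so precision that the design has already paid for is worth reporting. Naming the term in advance also removes a later choice about whether to include it.

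**Working it through.** **Inputs from the documents.** 105 participants, 35 per arm (1.1); 1:1:1 blocks within a two-level stratum (5.5); follow-up at weeks 12 and 24 (4.1); α 0.05 (10.4.2, taken as two-sided). Section 10.2 gives no power, SD or dropout, and no section says how strongly SNAP/WIC receipt predicts the outcome. There is no planned figure to reproduce.

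**Assumptions.** R², the share of week-24 variance of weight change explained by the stratum, is 2%, 5% or 10%. Half of participants receive SNAP/WIC. Within-stratum variance is the same at both visits. Simulations use a visit correlation of 0.7 and blocks of 3, 6 and 9.

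**Step 1: true standard error.** With the stratum balanced across arms it is σ√((1−R²)·2/35).

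**Step 2: reported standard error.** The random-intercept model, with change at weeks 12 and 24 as response, pools variance over both visits. Let the stratum gap at week 12 be a fraction f of the gap at week 24. The stratum then adds f²R² and R² at the two visits, on average R²(1+f²)/2. So

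reported/true = √{[1 − R² + R²(1+f²)/2]/(1 − R²)}.

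For f = 1 this is 1/√(1−R²). For f = ½ it is √{(1 − 0.375R²)/(1 − R²)}. The actual size of a nominal 5% test is 2[1 − Φ(1.96 × ratio)]. The stratum gap that R² implies is √(R²/0.25) in SD units.

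| R² | Gap (SD) | SE ratio, f = 1 | SE ratio, f = ½ | Test size, f = 1 | Test size, f = ½ |
|---|---|---|---|---|---|
| 2% | 0.28 | 1.010 | 1.006 | 4.8% | 4.9% |
| 5% | 0.45 | 1.026 | 1.016 | 4.4% | 4.6% |
| 10% | 0.63 | 1.054 | 1.034 | 3.9% | 4.3% |

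**Step 3: simulation.** Fitting the model without and with the stratum terms on complete data gives ratios of about 1.01, 1.025 and 1.056 for f = 1, and 1.006, 1.016 and 1.034 for f = ½. With 20% dropout and f = 1 they are 1.009, 1.024 and 1.051. At R² = 0 there is no gain or loss beyond 0.1%. A separate null simulation of one week-24 comparison rejected in 4.6%, 4.5% and 4.0% of trials without the stratum, and in 4.8%, 5.1% and 5.1% with it.

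**Step 4: in points of weight loss.** At an assumed SD of 5 points with complete data and f = 1, the 95% half-width is 1.96 × 5 × √(2/35) = 2.34. Multiplying by √(1−R²) gives 2.32, 2.28 and 2.22.

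**Step 5: which term recovers the gain.**
- *Change as response.* For f = 1 a stratum main effect recovers all of it. For f = ½ it leaves (¼)²R² = 0.0625R² in the residual, so the ratio is √{(1 − 0.375R²)/(1 − 0.9375R²)} = 1.006, 1.015 and 1.031. That is most of the gain.
- *Baseline kept as a repeated response, contrast = change from baseline to week 24.* This is a within-participant contrast, and a main effect constant over time does not touch its variance (ratio 1.000). If R² is the share of variance of change and the effect is full by week 12, the excess is √{(1 − R²/3)/(1 − R²)} = 1.007, 1.017 and 1.036. Only stratum-by-time removes it.
- *Treatment main effect averaged over weeks 0, 12 and 24*, one reading of 10.4.3. Here a stratum main effect does help: ratios 1.012, 1.031 and 1.065 in simulation with the week-0 response set to zero.

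**Step 6: the covariate rules.** In 36,000 simulated stratified allocations (30%, 50% or 70% SNAP/WIC, three assumed block sets) the chi-square p-value for a SNAP/WIC difference between arms never fell below 0.54. The missing-outcome rule selects the factor in 20–21% of trials when dropout is unrelated to it, and in 91–93% when dropout is 10% in one stratum and 30% in the other. Even then it enters a sensitivity analysis only.

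**The case against.** The strongest reply is that little turns on this. Every non-zero figure rests on an assumed R². At 2–5% the half-width moves by a few hundredths of a point in an exploratory trial with no stated power, and the point estimate is essentially unchanged. A test that stays at or below its nominal level is valid. All of this stands, and it is why the point is minor.

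Two further objections also stand. Section 10.4.2 leaves the response unclear, and the stratum terms that matter depend on it; the fix therefore covers both readings. The magnitude is worked out for weight change only. For quality of life, skin carotenoids and diet quality the direction is the same, but the size is not assessed. The imbalance result in step 6 depends on assumed block sizes and on a chi-square criterion, for which 10.4.2 sets no threshold.

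A reader might infer more than the documents support:
- *That the primary test is invalid, biased or has inflated type I error.* The effect runs the other way. In a deliberately adverse case, with dropout by stratum in opposite directions in two arms (10%/30% against 30%/10%), leaving the stratum out shifted the contrast by at most 0.05 SD and rejection stayed at or below 5.3%.
- *That 10% is an upper bound for R².* Nothing in the documents bounds it. At 20%, simulation put the standard error 11–13% too large and test size near 3%.
- *That a stratum main effect alone is always useless.* That holds only for the change-from-baseline contrast with baseline as a repeated response.

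**Conclusion.** The omission is real and minor. SNAP/WIC receipt is the only stratification factor, yet no primary, secondary or exploratory model names it, and the plan's covariate rules leave the primary result unadjusted. If it predicts the outcome, precision is slightly understated, by the amounts in the step 2 table; if it does not, nothing changes. Direction follows from the design and does not depend on the assumptions. Size depends on R² and on how far the stratum effect has developed by week 12, and the documents give neither. Correcting it is a nearly free improvement and does not rescue a faulty analysis.

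**What to change.** In 10.4.2 and 10.4.3, pre-specify the baseline SNAP/WIC stratum as randomised, and its interaction with time, as fixed effects. State that this is the stratum used at randomisation, not the status re-collected at weeks 12 and 24, which is measured after treatment has started.

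In the same edit, say whether the response is change at weeks 12 and 24 or includes baseline as a repeated measurement. With change as response, the stratum main effect does all or most of the work. Stratum-by-time is needed only if baseline is a repeated response and the contrast is change from baseline to week 24. Including both terms covers either case.

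The cost is wording and two degrees of freedom, or three with baseline as a response. The factor is already collected at week 0. If it explains nothing, adding it raises the standard error by about 0.1% with 20% dropout.
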